6.9.2.2 Other Adverse Events

The original terms used by investigators on the CRF will be translated to COSTART terms and grouped into body system and presented as frequency tables. For each and any immunization, the number and percent of subjects with adverse events will be tabulated, by group and by site. When adverse events occur more than once, the maximal severity and relationship to vaccine will be counted. Three summaries will be generated: (1) Serious adverse events (SAEs); (2) adverse events that are definitely, probably or possibly related to vaccination, and (3) adverse events that are remotely or not related to vaccination. Data listings of all adverse events will be provided by subject, as will subset listings summarizing subjects withdrawn from the study because of an adverse event.

6.9.2.3 Clinical Laboratory

Listings and descriptive statistics will be generated for all laboratory parameters that are abnormal, by group and site. Data listings will be provided by subject summarizing all abnormal values, by parameter (WBC count, hemoglobin, platelet count, ALT, creatinine, U/A).

6.9.3 Immunogenicity

Lymphocyte proliferation will be described as a stimulation index (LSI = CPM of test antigen/Medium Control). For each group geometric mean LSI, median minimal and maximal LSI, as associated 95% confidence intervals will be calculated. The primary timepoint of interest for antibody responses will be one month post immunization #4; cellular responses will be measured as described in section 6.7. The following definitions establish discrete categorical data (response present vs absent) for significance testing:

Cellular: A positive lymphoproliferative response is present if an $LSI \ge 5$ to an HIV-specific vaccine component develops at 2 timepoints post vaccination.

A CTL response is present if HIV-antigen specific lysis at two effector: target (E:T) ratios is > 10%. The response is CD8+ T cell mediated if, on subsequent testing (depletion assay), depletion of CD8+ T cells removes 50% of the HIV antigen specific lytic activity, while removal of CD4+ cells maintain at least 5% HIV specific lysis. Likewise, The response is CD4+ T cell mediated if, on subsequent testing, depletion of CD4+ T cells removes 50% of the specific lytic activity, while removal of CD8+ T cells maintain at least 5% specific lysis.

Cumulative % bulk CTL response is calculated as follows: number of participants with a CTL response to any vaccine component on any study day/total # of participants X 100 (for vaccine and placebo groups). Cumulative % CD8+ T cell mediated CTL response is calculated as follows: number of participants with a CD8+ T cell specific CTL response to any vaccine component on any study day/total # of participants X 100 (for vaccine and placebo groups). CTL responses will be categorized for the purpose of enumeration as: 1) high response, occurring on 5 or more occasions in an individual during the study, 2) medium response, occurring on 3-4 occasions and 3) low response, occurring on 1 or 2 occasions.

ELISPOT assay:

The number of cytokine (IFN-g or other) spot forming cells $(SFC)/10^6$ PBMC will be assessed to HIV vaccine components. Responses are calculated by subtracting the background SFC (in response to media alone) from the # of SFC to HIV vaccine components.

A positive **ELISPOT** response is defined by an absolute number of SFC

> 20 SFC/10⁶ PBMC and SFC to HIV vaccine components at least twice those of background.

Humoral: A positive neutralization response is defined as >50% reduction in HIV gag antigen (vaccine related HIV strains vs normal human serum) in a continuous T cell line based neutralization assay

For each group, least squares geometric mean titer (GMTs), associated 95% confidence intervals, and median, minimal and maximal titer will be calculated to MN, LAI, gp120/160 antigens, by ELISA. Neutralizing antibody titer will be similarly measured to TCLA viruses and to select primary isolates.

Chi-square and Fisher's exact tests will be employed. All tests will be conducted as two-sided at the 0.05 significance level. Statistically significant results will be annotated by their degree (*p<0.05;**p<0.01;***p<0.001).

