6.3.2 Ancillary Immunogenicity Studies

Measurement of breadth of antibody response by characterizing

-serum binding and neutralizing antibody to vaccine component antigens, including anti-ALVAC antibodies (ELISA)

-anti-KLH binding antibodies (ELISA) in dendritic cell arm only

-neutralizing antibody activity against primary isolates in vaccinee sera that display high level of neutralizing activity against the HIV-1 MN strain.

Measurement of breadth of cellular response by quantifying and characterizing

- modified bulk CTL assay using autologous dendritic cells for in vitro stimulation

- identification of selected cytokine/chemokine production from supernatants from LPA

- mapping of cross-reactive cellular epitopes by measuring lymphocyte proliferation and CTL activity against proteins and/or peptides from diverse HIV-1 subtypes.

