4. Obtain interim history and physical, including vital signs and abbreviated risk assessment.

5. Perform risk behavior avoidance counseling and provide HIV test counseling.

6. Collect samples for HIV serology (1 ml red top).

7. Collect samples for immunogenicity (40 ml anticoagulated blood): LPA, neutralizing antibody, CTL, and ELISPOT. Separately and additionally, draw 3 ml of blood into a heparinized pediatric tube (no substitutions) PRIOR to immunization (whole blood ICC).

8. Administer vaccine injection(s) into the deltoid muscle (IM), or intradermally on the volar aspect of the arm (ID). The autologous DC are prepared from the pre-study leukopheresis. The DC are counted, checked for sterility, identity and potency and after being cleared for release, injected into the superficial subcutaneous space on the ventral inner aspect of the arm in two 0.2 ml aliquots. See details in **Appendix A** for specifics on dendritic cell release criteria, counts and maturity. Examine the injection sites for local reactions at 60 minutes post-injection and instruct subject in the evaluation of these local reactions; observe and instruct while the subject takes temperature (as guided for subsequent evaluations); enter findings on appropriate CRF.

9. Subjects will record daily symptoms for 7 days post-immunization (including the day of immunization), and will be instructed to contact the investigator if any untoward effects occur.

24-48 hour contact after the first immunization:

Subjects will be contacted by staff within 24 to 48 hours post-immunization (by telephone, by home visit, or by the other prearranged mechanism) to determine whether adverse effects have occurred. Subjects will be queried using a predetermined review of systems/reactogenicity worksheet. If the adverse effects experienced by the volunteer are deemed "moderate", he/she will be asked to return to clinic for evaluation by the investigator. Additional contacts will be arranged as indicated.

Visit 3: Day 14 (+/-4 days) after initial vaccination: Safety Evaluation

1. Collect diary, obtain interim history and physical.

2. Collect sample for CBC.

3. Collect sample for Chem-7, LFT's (Na, K, Cl, HCO3, Cr, BUN, Glc, AST, ALT, Total Bili, alk phos).

4. Collect urine for dipstick. If urine protein or blood is 1+ or greater, obtain a complete UA.

Visit 4: Day 28 (+/- 7 days) after initial vaccination:

Second vaccination

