6.6 Study Variables and Their Measurement

6.6.1 Immunogenicity Variables

- 1. Cellular Immune Response to HIV-1 Antigens
 - a. Cells for the assessment of lymphocyte proliferation to HIV gp160 MN and gag IIIB protein will be collected on days 0, 14, 28, 42, 60, 104, 120, 194, 264, and 354.
 - b. Cells for the assessment of CTL activity and ELISPOT assay for interferon-g will be collected days 0, 14, 28, 42, 60, 104, 120, 194, 264, and 354.
 - c. Cells for the enumeration and identification of antigen specific interferon-g production using flow cytometry will be collected on Day -10, 28, 120, 194, 264 and 354.
- 2. Humoral immune responses to HIV

a. Antibody responses to homologous HIV-1 MN, gp120, and p24III-B and other non-hologous HIV-1 env antigens and peptides will be evaluated using plasma collected on days 0, 28, 60, 120, 194, 264, and 354.

b. Neutralizing antibody to HIV-1 MN strain, selected primary isolates, and other TCLA strains will be performed by the Immunology Laboratory at WRAIR, Rockville, MD.

3. Ancillary Studies

Human specimens collected under this protocol may be used to address other relevant questions regarding HIV-1 immunity if cells are available and CTL or neutralizations are elicited. Specifically, cells may be used to compare pre- and post-immune responses, compare assay methods of determination of cytotoxicity, characterize cytokine production, detect evidence of intracellular vaccine or cellular activation as a result of exposure to vaccine, or check for expression of vaccine components on the surface of autologous DC exposed to vCP205. Additionally, peripheral blood cells will be studied for evidence of sensitization to the vaccine (anti-ALVAC antibodies) and for evidence of primary cellular and humoral immunity against the test antigen KLH. Most methods described herein are standard immunologic techniques, however should new techniques become available to delineate HIV-1 immunity, these may be used as well. Aventis Pasteur, the US Army Medical Research and Material Command, and Rockefeller University will be informed of and consulted regarding these ancillary studies. These results will be discussed by the aforementioned parties prior to public disclosure.

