6.6.1.2 Sample collection

Laboratory study	Type	Storage	Tube*	Amount
Hematology	blood	fresh	EDTA	3 ml
Chemistry	serum	fresh	red	3 ml
HIV Western blot	serum	fresh/frozen	red	1 ml

Serology	serum	fresh/frozen	red	1 ml
gp120/41 antibody	ser/plas	frozen	heparin	10 ml
Lymphocyte proliferation	blood	fresh/frozen	heparin	10 ml/8 ml
Cytotoxicity assay	blood	fresh/frozen	heparin	10 ml/8 ml

*Equivalent, appropriate substitutions to tube types are allowed

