6.7 Procedural Flow Chart

6.8 Volunteer's Vaccine Schedule

6.9 Statistical Methods and Determination of Sample Size

6.9.1 Statistical Plan: Design and Sample Size Calculation

The data will be analyzed by DCAC. Any data analyses carried out independently by investigators should be submitted to WRAIR before publication or presentation.

The trial as designed has 3 groups:

Group I: Subcutaneous reinjection of *ex vivo* generated vCP205 transfected autologous dendritic cells Groups II and III: Intradermal or intramuscular injection of vCP205

The primary safety measurements include data from the clinical laboratory tests, observed immunization reactions (local and systemic) and adverse events. The primary immunogenicity data focus on cellular responses which will be assayed by both blastogenesis (lymphocyte proliferation) and cell mediated cytotoxicity.

This study is intended as a proof-of-concept to test the safety of the dendritic cell and ID delivery routes. It is not a definitive hypothesis testing study aimed at evaluating the relative immunogenicities (as measured by CTL response) of the IM, ID and DC arms. Despite this, we were able to determine the power with which differences between the DC arm and the better of the IM or ID arms could be detected. Assuming 100% (8 of 8) CTL response in the DC arm and 38% (3 of 8) response in the IM or ID arm, we would have approximately 70% power to detect a true difference in CTL response between the two arms if one actually exists. Additional information provided by immunomonitoring using ELISPOTs and intracellular flow cytometry (for IFN-gamma production) and blastogenesis assays (lymphocyte proliferation), we believe, will allow the study to determine if DC or ID routes are substantially better than the IM route.

All subjects receiving at least one injection of vaccine will be included in the safety and tolerability analyses. All data exclusions, including premature terminations, will be detailed and tabulated according to vaccine group. Data listings will include all subjects.

Demographic data obtained during the baseline visit will be listed for each subject. Summary statistics will be tabulated for each vaccine group. Subjects will be assessed for comparability at baseline. Descriptive statistics will be presented for continuous variables (age, height, weight). Frequency counts and percents will be presented for categorical variables (age, sex, and race).

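### The neutralization responder rule in 6.9.3 refers each sample only to normal human serum and ignores the volunteer's own Day 0 sample, so reactivity present before vaccination can be scored as a response.

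*Protocol*

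**What the plan says.** Section 6.9.3 introduces its responder rules with this statement: "The following definitions establish discrete categorical data (response present vs absent) for significance testing". Under the humoral heading it continues: "A positive neutralization response is defined as >50% reduction in HIV gag antigen (vaccine related HIV strains vs normal human serum". Chi-square and Fisher's exact tests follow, two-sided at 0.05.

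In section 6.5.6, item 7 of Visit 2 (Day 0) reads "Collect samples for immunogenicity (40 ml anticoagulated blood): LPA, neutralizing antibody, CTL, and ELISPOT". The injection is item 8 of the same visit, so the draw comes first.

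On the specimen, section 6.6.1 item 2a says that antibody responses to env and p24 antigens "will be evaluated using plasma collected on days 0, 28, 60, 120, 194, 264, and 354". Item 2b, on neutralization, names no specimen: "Neutralizing antibody to HIV-1 MN strain, selected primary isolates, and other TCLA strains will be performed by the Immunology Laboratory". Section 6.3.2 refers to "neutralizing antibody activity against primary isolates in vaccinee sera that display high level of neutralizing activity". The table in 6.6.1.2 has a row for "gp120/41 antibody" that allows serum or plasma in a heparin tube, and no row for neutralization.

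On standing, 6.3.2 lists antibody work as ancillary, and 6.9.1 states: "The primary immunogenicity data focus on cellular responses".

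**The concern.** A vaccine response is a change from before to after vaccination. This rule measures something else: the difference between the volunteer's sample and serum from another source. Anything in the volunteer's sample that lowers the gag signal is counted, whether or not it was there before the first dose. Because the rule produces a yes/no variable for significance testing, a misclassified volunteer enters the count at full weight.

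Two results are exposed. One is the absolute responder rate per arm, which readers of a small phase I study are likely to quote. The other is the ability to tell vaccinees from controls, because background positives in both groups shrink the difference. Section 4 describes neutralizing titres after ALVAC-HIV alone as modest, so true responses may lie near the cut-off, where background matters most.

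**Working it through.** **1. Does any part of the rule use baseline?** No. It has a threshold (above 50%) and a reference (normal human serum). It does not require a negative Day 0 result, or a change from Day 0. Two other rules in 6.9.3 do more. The lymphoproliferative response has to arise after vaccination and is scaled to a medium control, and ELISPOT subtracts the media-only count. The CTL rule, like the neutralization rule, has no baseline term.

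**2. Is an own baseline sample available?** Yes. In 6.5.6 neutralizing antibody is listed at Visits 2, 4, 6, 9, 11, 12 and 13, which are days 0, 28, 60, 120, 194, 264 and 354. These are the days given for antibody responses in 6.6.1 item 2a.

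**3. What does ignoring it do?** Let s be the true response rate in vaccinees and f the proportion whose sample passes 50% for reasons unrelated to vaccine. Take f as equal in vaccinees and controls and independent of true response.

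- Observed rate in vaccinees: s + (1 − s)f
- Observed rate in controls: f
- Observed difference: s(1 − f)

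If s = 0, both groups show f and the difference is zero, so no false vaccine effect is created. If s = 50%, f = 10% gives 55% against 10% (difference 45 points), and f = 30% gives 65% against 30% (difference 35 points). The rate is inflated and the contrast diluted.

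**4. Illustration.** The protocol states no figure for neutralization to reproduce, and it gives no f; the values below are assumptions. Group sizes are 8 vaccine and 4 control per arm (6.5.3). The chance of at least one background positive is 1 − (1 − f)^n. Power is exact, summed over both binomials, for a two-sided Fisher test at 0.05. Pooling the arms (24 against 12) is done here only to show the effect in a larger comparison.

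| f | Expected background positives in 8 (8f) | At least one in 8 | At least one in 4 | Power 8 v 4, s = 75% | Power 8 v 4, s = 50% | Power 24 v 12, s = 50% |
|---|---|---|---|---|---|---|
| 0 | 0 | 0 | 0 | 0.367 | 0.035 | 0.968 |
| 5% | 0.4 | 34% | 19% | 0.345 | 0.040 | 0.858 |
| 10% | 0.8 | 57% | 34% | 0.322 | 0.044 | 0.763 |
| 20% | 1.6 | 83% | 59% | 0.275 | 0.050 | 0.578 |
| 30% | 2.4 | 94% | 76% | 0.227 | 0.054 | 0.418 |

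Within one arm, power is low whatever f is. The dilution shows clearly only in the pooled comparison.

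**5. Can the controls measure f?** Poorly. With 0 of 4 positive, the exact two-sided 95% upper limit is 1 − 0.025^(1/4) = 60%. With 0 of 12 over all arms it is 1 − 0.025^(1/12) = 26%.

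**6. Specimen wording side by side.**

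| Section | Specimen |
|---|---|
| 6.5.6, Visit 2 (neutralizing antibody named) | anticoagulated blood |
| 6.6.1 item 2a (binding antibody) | plasma |
| 6.6.1 item 2b (neutralization) | not stated |
| 6.3.2 (neutralization) | sera |
| 6.6.1.2 (gp120/41 row) | serum or plasma, heparin tube |
| 6.9.3 (reference) | normal human serum |

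The draws favour plasma, but the protocol does not settle it.

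**The case against.** A reader might go further and infer that heparinised plasma is tested against serum, so that non-specific plasma inhibition is credited to the vaccine. The documents do not support that reading, for three reasons:

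- The specimen is not fixed. The plasma statement belongs to the binding-antibody item, and 6.3.2 speaks of sera.
- Nothing in the protocol says that plasma or anticoagulant inhibits this assay. Section 6.6.1.1 allows tube substitution only where it does not interfere with the study in question.
- The sign is unknown. Suppose the test sample has extra non-specific inhibition m relative to the reference, acting multiplicatively. The specific neutralization needed to pass is then 1 − 0.5/(1 − m). At m = +20% this is 37.5%, a looser threshold; at m = −20% it is 1 − 0.5/1.2 = 58.3%, a stricter one.

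The wider defence is also fair. Normal human serum is a reasonable assay control. Each arm has randomised, blinded controls sampled on the same schedule, so a shared background cannot create a vaccine effect. Day 0 is an assay time point, so background would be visible to anyone who looked. Titres are summarised as well, so the humoral result does not rest on the yes/no call alone. The study describes itself as descriptive, and neutralization is ancillary.

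All of this limits the consequence. It does not supply the missing baseline: a visible Day 0 positive would still meet the rule as written, and four controls per arm cannot pin down the background rate.

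**Conclusion.** The point holds as a minor one. As written, the rule can count a volunteer as a responder for reactivity that preceded vaccination, although the sample that would show this is already collected for the assay. Individual calls and absolute responder rates can be inflated, and vaccine-versus-control contrasts diluted. The randomised within-arm comparison is not pushed toward a false vaccine effect. The specimen wording also needs to be reconciled.

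The size cannot be estimated from the protocol. The figures above rest on an assumed f of 0 to 30%, equal in vaccinees and controls, independent of true response and still present at the later sample. If no volunteer is reactive at Day 0, the omission costs nothing. The primary cellular measures are unaffected.

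**What to change.** In 6.9.3, define a positive post-vaccination neutralization response as more than 50% reduction relative to the same volunteer's Day 0 sample, in the same matrix and the same run. Keep normal human serum as the run control. If that is not practicable, at least require that the Day 0 sample be negative by the existing rule. This weaker version removes volunteers who already pass at baseline, but leaves background below the threshold uncorrected. Name one matrix for neutralization and use it consistently in 6.3.2, 6.5.6, 6.6.1, 6.6.1.2 and 6.9.3.

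The cost is a few sentences of text and one stored Day 0 specimen re-run per volunteer alongside the later samples. No new blood draw is needed. The drawback is that a call referred to baseline takes on some assay noise from the Day 0 measurement.

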7. COMPENSATION, INSURANCE, INDEMNITY

7.1 Information on compensation, insurance and indemnity

Information on compensation, insurance and indemnity will be supplied to the investigator in the Clinical Study Agreement. Volunteers will be compensated for the last screening visit and for each scheduled vaccine visit according to the following schedule (not to exceed, unless receipt is presented): for each blood draw the volunteers will receive \$50.00. For each leukopheresis the donor will receive \$300.00. This means that each volunteer in the trial may be compensated up to \$1250.00.

7.2 Advocacy

All volunteers will receive an individual identification card indicating their status as a vaccine trial participant. All volunteers will be counseled periodically regarding the potential for testing positive on routine screening tests for HIV-1 as a consequence of participation in this trial and receiving this vaccine product. All volunteers will be offered further confirmatory testing and certification as to the nature of their vaccine trial participation whenever needed to address complications arising at home, at work or in the community which could arise from routine screening for HIV-1.

8. VACCINE ACCOUNTABILITY

The investigator must maintain accurate records of dates and quantities, and lots of product(s) received, to whom dispensed (subject-by-subject accounting), and accounts of any product accidentally or deliberately destroyed. The investigator must retain all unused or expired product until the study monitor has confirmed accountability data.

At the conclusion of vaccine administration, all vaccine supplies (including used and unused vials) will be disposed of according to the procedure agreed upon. An overall summary of all vaccine supplies received, used and returned must be prepared at the conclusion of the study.

9. LABORATORY REQUIREMENTS

Clinical laboratory evaluations for safety will be performed at various time points during the trial.

10. CASE REPORT FORMS

Case report forms (CRF) will be provided for each subject. Correction to data on CRFs may be made only by putting a line through the incorrect data and writing the correct values, allowing the original text to remain legible. Each correction should be initialed and dated by the person making the change. If corrections are made after review and signature by the investigator, he/she must be made aware of the changes and document this awareness.

It is the policy of WRAIR that the study data must be verifiable to the source data, which necessitates access to all original recordings, laboratory reports, and subjects' records. The investigator must therefore agree to allow access to subjects' records, and source data must be made available for all study data.

